8.3 INTERIM ANALYSES

Interim analyses using an O'Brien-Fleming boundary will be conducted with the goal of terminating accrual early to accept or reject the null hypothesis of no difference in survival. Given the inflated type I error rate for this Phase 2 study, early termination will only be considered if it appears that the addition of BMX-001 treatment to radiation and temozolomide is decreasing survival. The interim analysis will be conducted to determine whether the addition of BMX-001 is possibly detrimental to the survival of patients.

8.3.1 INTERIM ANALYSIS #1

The study was originally designed with one interim survival analysis after approximately 42 deaths. The decision rule for accrual suspension was defined by the O'Brien-Fleming spending function and is dependent upon the number of deaths that will have been reported by the time of the interim analysis. If the boundary was crossed, accrual was to be suspended while all other data (e.g., cognitive function data) is reviewed to determine whether accrual should be permanently terminated.

The first interim analysis was conducted in December 2021 when 46 deaths had been observed in the ITT population (20 in Arm A and 26 in Arm B). The study was not terminated early as a result of the first interim analysis.

8.3.2 INTERIM ANALYSIS #2

An unplanned interim analysis was conducted in March 2022 to support an FDA application for breakthrough therapy designation. That analysis was conducted when 54 deaths had been observed among treated subjects (22 in Arm A and 30 in Arm B). The study was not terminated early as a result of the first interim analysis.

8.3.3 PRIMARY ENDPOINT ANALYSIS

After these 2 interim analyses, no further interim analysis will be conducted until the primary endpoint analysis. The primary endpoint analysis is scheduled to occur after 84 deaths have been observed.

8.4 POWER OF SURVIVAL COMPARISONS & FINAL ANALYSIS

The primary goal of the Phase 2 portion of this study is to assess the effect of BMX-001 treatment in conjunction with standard of care treatment consisting of temozolomide and radiation on the survival of patients newly diagnosed with grade III or IV glioma.

8.4.1 ORIGINAL POWER ANALYSIS

With standard treatment, the median survival of Grade IV patients is 14.6 months, and the median survival of Grade III is approximately 36 months. Before study activation, we anticipated that approximately 10% of patients to be Grade III. With 10% of patients as grade III, we estimated that the overall median survival with standard treatment to be roughly 16.7 months

Though this Phase 2 study is comparative, the goal is to determine whether BMX-001 is worthy of further investigation in combination with standard RT and TMZ treatment. Many aspects of the new treatment will be considered in the decision-making concerning further investigation, including relative toxicity and ease of treatment administration. As a Phase 2 study, there is a need to constrain the sample size requirements at the expense of either an increased false negative or false positive rate. A false-positive rate of 0.2 will be used to test the primary statistical hypothesis while maintaining reasonably high power [3-5].

The power of a statistical comparison of survival is a function of the number of deaths observed. In order that a 1-tailed logrank test conducted at the 0.2 level to have 90% power to detect a hazard ratio of 0.63, 84 deaths need to be observed among the 160 randomized patients. Under the assumption that survival is exponentially distributed, this hazard ratio represents an increase in median survival from 16.7 to 26.5 months.

8.4.2 REVISED POWER ANALYSIS

In actuality, approximately 20% of patients enrolled were Grade III. With 20% of patients to be grade III, we estimate that the median overall survival with standard of care treatment to be roughly 18.9 months.

With these modifications the power analysis has been revised:

The power of a statistical comparison of survival is a function of the number of deaths observed. In order that a 1-tailed logrank test conducted at the 0.2 level to have 90% power to detect a hazard ratio of 0.63, 84 deaths need to be observed among the 160 randomized patients. Under the assumption that survival is exponentially distributed, this hazard ratio represents an increase in median survival from 18.9 to 30.0 months.

8.5 ADDITIONAL ANALYSES, INCLUDING SUBGROUP ANALYSES

The analyses described in Section 8.2 will be repeated within the treated population.

Within the ITT and treated patient populations, various subgroups analyses will be conducted. Subgroups will be defined by the following factors:

- Original histologic WHO grade (III or IV)
- New histologic WHO grade (III or IV)
- MGMT (present or absent)
- IDH status
- 19q FISH
- Age: subjects > 65 at time of consent
- Others as needed

The Kaplan-Meier estimator will describe the survival within each combination of histologic grade and treatment arm. Several analyses may be conducted:

1. Within each subgroup defined by the variables above, Cox proportional hazards model will assess the effect of treatment on survival.

- The Cox model will explore the joint effect of the clinical predictor and treatment assignment, and possibly their interaction. Such an analysis will explore whether the effect of BMX-001 treatment is consistent across levels of the clinical predictors.
- 3. The Cox model may also explore the joint effects of age, gender, histologic grade, MGMT, and other prognostic factors on survival.

9 SECONDARY OBJECTIVE: COGNITION

The first secondary objective involves an assessment of whether the addition of BMX-001 to standard RT and TMZ treatment for patients newly diagnosed with HGG has an impact upon cognition. The BAC App (provided by VeraSci) and paper forms (HVLT-R, COWA, TMT) were used to assess patient cognition.

BAC App (i-Pad based testing)

The BAC battery of tests was implemented through an iPad-based app called the BAC App (the vendor that provides this is called VeraSci, previously called NeuroCog). Subtests included:

- Verbal Memory
- Digit Sequencing
- Token Motor
- Semantic Fluency
- Letter Fluency
- Symbol Coding
- Tower of London

Beginning at baseline, the BAC will be obtained longitudinally:

- Screening (for the baseline assessment),
- After standard RT and TMZ (within 2 to 4 weeks), and
- Approximately every 8 weeks when a subject returns for a Standard of Care visit during adjuvant TMZ.

Paper cognitive testing

Paper forms were used to assess patient cognition using the following instruments:

- Hopkins Verbal Learning Test-Revised (HVLT-R)
- Trails Making Test Parts A and B (TMT), and
- Controlled Oral Word Association Test (COWA)

Timepoints completed:

- Baseline (prior to the start of RT)
- Standard of care visit before the start of the first cycle of adjuvant temozolomide,
- Standard of care visits that are 6 and 12 months from the completion of radiotherapy/ chemotherapy.

When a subject came off study for disease progression before the approximate 6 and 12 months post completion of treatment timepoint, cognitive testing was supposed to continue and be collected at those timepoints and if present will be included.

The analysis of Cognition data will focus on the cohort of patients who were treated. Typically, patients who were not treated did not provide any cognitive data follow-up.

9.1 DROP-OUT PATTERNS

The ultimate goal of this objective is to compare groups with respect to longitudinal changes in cognition over time. Unfortunately, due to the patient population that are eligible to participate in this study, a significant amount of the follow-up cognitive assessments may be missing due to health decline, disease progression, and death. Some of the missing data may be intermittently missing (i.e., missing observations between observed assessments); however, much of the missing data will be "drop-out" (i.e., subject permanently drops out of longitudinal assessment). The pattern of "drop-out" in the two treatment arms will be assessed.

The proportion of patients within each treatment arm who lack assessments after the baseline assessment will be determined and compared using a chi-square test. We will also explore whether there are subgroups defined by clinical, cognitive, or HRQoL data that are predictive of a subject lacking a post-baseline assessment.

Drop-out may also occur after one or more follow-up assessments are completed. The relationship between the time of the last completed assessment and treatment group will be assessed via a contingency table and chi-square test.

9.2 ENDPOINT

Though the study is a longitudinal analysis, the initial focus of the analyses of this objective is an examination of the mean change in cognitive functioning between baseline and week 24 (occurs after completion of RT) within each treatment arm. The baseline measure is the last assessment obtained before initiation of standard chemoradiation.

There is variability in the timing of follow-up measurements. For the purpose of this analysis a +/- 4 week window will define the 24 week assessment.

Clearly a patient without an assessment post-baseline will not be included in these analyses. Analyses described in Section 9.1 explore how the patients excluded from analyses differ from those who are included in analyses.

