### **Table 1: Phase 1 Objectives and Endpoints**

### Table 2: Phase 2 Objectives and Endpoints

	Objective	Endpoint	Analysis
Primary	To assess the efficacy of standard RT and TMZ in combination with BMX- 001 compared to standard RT and TMZ alone in newly diagnosed HGG patients based upon overall survival (OS).	Median OS, where OS is defined as the time to death from randomization.	See Section 16.5.1
Secondary	To examine the impact on cognition of BMX-001 in combination with standard RT and TMZ in treatment of newly diagnosed HGG patients.	Mean change between baseline and week 24 in normalized scores for cognition using standardized cognitive tests and BAC This includes Hopkins Verbal Learning Test-Revised, Trails Making Test Parts A and B, and Controlled Word Association Test and BAC (VeraSci) consisting of seven tests that measure verbal memory and learning, working memory, motor function, verbal fluency, speed of processing, and executive function.	See Section 16.5.2
Secondary	To assess protection of bone marrow against chemotherapy induced thrombocytopenia in patients being treated with standard RT and TMZ in combination with BMX-001 compared to standard RT and TMZ alone in newly diagnosed HGG patients.	Proportion of patients with thrombocytopenia grade 3 or 4 adverse event during standard RT and TMZ treatment. Proportion of patients with a platelet count below 100,00 during standard RT and TMZ treatment and who had suspension of TMZ therapy.	See Section 16.5.2.2
Secondary	To assess the safety and tolerability of standard RT and TMZ in combination with BMX-001 compared to standard RT and TMZ alone in newly diagnosed HGG patients.	Proportion of subjects who experience grade 3 or 4 adverse event during standard RT and TMZ treatment. Proportion of subjects who experience grade 3 or 4 adverse event that are definitely, possibly, or probably related to BMX-001 treatment.	See Section 16.5.2
Secondary	To assess the efficacy of standard RT and TMZ in combination with BMX- 001 compared to standard RT and TMZ alone in newly diagnosed HGG patients based upon progression-free survival (PFS).	Median PFS, where PFS is defined as the time between initiation of protocol treatment and the first recurrence of disease or death.	See Section 16.5.2

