s These assessments should be completed prior to other study-related evaluations at study visits, if at all possible. CNS Vital Signs®(Phase 1) /NeuroCog BAC App (Phase 2) will be done screening (baseline), and then approximately every 8 weeks when a subject returns for a Standard of Care visit during the Adjuvant Phase.

t. Hopkins Verbal Learning Test-Revised (Forms 1, 2, and 3), Trails Making Test Parts A and B, and Controlled Word Association Test will be performed only at baseline, the standard of care visit before the start of the first cycle of adjuvant temozolomide, and the standard of care visit that is 6 and 12 months from the completion of radiotherapy/chemotherapy. See appendices for appropriate versions of these forms to use.

u Hair loss evaluation includes subjective description and photos.

v Patients will continue to complete visits in the adjuvant cycle for up to the 12 planned cycles, as long as they do not have progression on MRI (even if they stop taking adjuvant TMZ). Cognitive testing will be completed even after progression is noted.

w Collection of Gender, Race, Ethnicity, Education completed, employment, and smoking status to be obtained at screening.

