Among the secondary endpoints are two that are of particular interest: cognitive function and thrombocytopenia. The mean change in cognitive functioning between baseline (enrollment) and week 24 within each treatment arm will be computed, and analysis of covariance will be conducted to compare groups with respect to that change. Treatment group assignment will be included in the model as a predictor, and the baseline measure of cognitive function will be included as a covariate.

The proportion of patients who experience grade 3 or 4 thrombocytopenia during concurrent temozolomide and radiation, a period that terminates 2 weeks after completion of radiation treatment, will be summarized. A chi-square test will be conducted to compare the prevalence of such thrombocytopenia observed in patients with and without BMX-001.

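### The week-24 cognition window has no stated time origin and, on its natural reading, does not fit the schedule of the paper tests (HVLT-R, TMT, COWA)

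*SAP*

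**What the plan says.** Protocol Table 2 defines the cognition endpoint as "Mean change between baseline and week 24 in normalized scores for cognition using standardized cognitive tests and BAC" and lists HVLT-R, TMT Parts A and B and the word association test beside the BAC. SAP 9.2 repeats the time point as the "mean change in cognitive functioning between baseline and week 24 (occurs after completion of RT) within each treatment arm" and adds the window: "For the purpose of this analysis a +/- 4 week window will define the 24 week assessment". The overview in SAP 4 words it as "The mean change in cognitive functioning between baseline (enrollment) and week 24 within each treatment arm will be computed".

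The two groups of instruments follow different schedules. Under SAP 9 the BAC is given at screening, 2 to 4 weeks after chemoradiation, and then about every 8 weeks. After baseline the paper tests are given at the "Standard of care visit before the start of the first cycle of adjuvant temozolomide" and at the "Standard of care visits that are 6 and 12 months from the completion of radiotherapy/ chemotherapy". Footnote t of Protocol Table 4 restricts them to these visits and places the late ones at "the standard of care visit that is 6 and 12 months from the completion of radiotherapy/chemotherapy". No paper-test visit is labelled week 24.

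SAP 9.4.2 reports that 94 patients (52 in Arm A, 42 in Arm B) have baseline and follow-up measurements once the window is applied, and derives a detectable difference of 17.6 units. It names neither the instrument nor the origin used for the count.

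**The concern.** One window is applied to instruments that are measured at different times. If the scheduled late paper-test visit lies outside the window, the week-24 ANCOVA for HVLT-R, TMT and COWA contains only patients whose visit came at the wrong time. They would be a small and probably unrepresentative group.

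Protocol 16.5.2.1 treats cognition as the key secondary objective. Protocol 7.3 singles out HVLT-R, Trails B and COWA as the tests that best show decline after radiotherapy and rests its early Phase 1 impression of benefit on them.

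The trial is open-label, and the window has already been applied to data by arm. While the origin stays unwritten, the choice of which visits, patients and instruments enter this analysis can be made after the data have been seen.

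**Working it through.** **The plan's own figure.** Inputs from SAP 9.4.2: SD 30, arms of 52 and 42, two-sided 0.05, 80% power.

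- Normal approximation: (1.96 + 0.84) × 30 × √(1/52 + 1/42) = 2.80 × 30 × 0.2075 = 17.4.
- Two-sample t-test (noncentral t): 17.62. Power at 17.6 is 0.799.

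The 17.6 reproduces. So does the figure of 15.5 in SAP 9.4.1: with 60 per arm the t-test gives 15.47.

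**Timing inputs.**

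- Window: 24 ± 4, so weeks 20 to 28 (SAP 9.2).
- Radiotherapy: 30 to 33 fractions at 5 per week in under seven weeks (Protocol 9.1.8.1). This is 30/5 = 6.0 to 33/5 = 6.6 weeks, with 7 as a limit.
- Six months: 26 weeks by the calendar, or about 24 weeks by the convention in footnote h of Protocol Table 4.

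**Counted from the start of radiotherapy.** Paper visit = length of radiotherapy + six months.

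| Radiotherapy (weeks) | 6 months = 24 weeks | 6 months = 26 weeks |
|---|---|---|
| 6.0 | 30 | 32 |
| 6.6 | 30.6 | 32.6 |
| 7.0 | 31 | 33 |

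Every entry is past week 28, by 30 − 28 = 2 to 33 − 28 = 5 weeks. A visit 2 weeks early reaches the limit in one cell only (30 − 2 = 28). Counting from an enrolment up to 3 weeks before radiotherapy moves the 6-week row to as late as 33 or 35. The pre-adjuvant visit, 2 to 4 weeks after radiotherapy, falls at weeks 8 to 10 and is also outside. The nominal BAC visits for a 6-week course fall at weeks 8–10, 16–18 and 24–26, so the BAC does have a visit in the window.

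**Counted from the end of radiotherapy.** The 6-month paper visit is at week 24 or 26. With ± 2 weeks that is 22–26 or 24–28, inside the window. The nominal BAC visits are at 2–4, 10–12, 18–20 and 26–28.

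**Which origin the text supports.** For the start of radiotherapy or enrolment:

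- Protocol Table 4 numbers its weeks through chemoradiation, with radiotherapy filling the first six. Protocol 13.3 adds two further weeks of BMX-001 in Arm A.
- SAP 4 ties baseline to enrolment in the same phrase as week 24.
- Testing 2 weeks after radiotherapy and then every 8 weeks gives weeks 8, 16 and 24 from its start. From its end the same grid is 2, 10, 18 and 26, without a week 24.
- The remark in SAP 9.2 that week 24 comes after radiotherapy says nothing if the count begins at the end of radiotherapy.
- SAP 17.1 and Protocol 13.8.10 count the 24-week imaging from the start of chemoradiation.

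For the end of radiotherapy: footnote h of Protocol Table 4 puts that same imaging at six months after treatment and glosses this as about 24 weeks.

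**The case against.** The strongest reply is that the SAP never defines the origin, so a scheduling failure is inferred rather than written. Table 4 numbers weeks only to 8 and then groups everything from week 9 on. The mention of enrolment in SAP 4 may only label the baseline measurement. Footnote h equates six months after treatment with about 24 weeks, and on that origin one window serves all four instruments. This stands as far as it goes: the end-of-radiotherapy reading cannot be excluded. It does not remove the point. Footnote h concerns imaging only, Protocol 13.8.10 and SAP 17.1 contradict it for that same imaging, and a reader would still have to guess the origin.

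A reader might also infer that the paper tests drop out of the cognition analysis. The documents do not support this. SAP 9.2 makes week 24 the initial focus only, SAP 9.3 adds a longitudinal pattern-mixture model, and SAP 9 includes the 6- and 12-month tests done after progression where they exist. Only the week-24 ANCOVA is affected.

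Nor can one infer that the 94 patients or the 17.6 units are wrong. The calculation reproduces, and SAP 9.4.2 does not claim it for any particular paper test.

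**Conclusion.** The point holds in this form: SAP 9.2 sets a single week 24 ± 4 window without an origin, and on the better-supported origin the window does not match the paper-test schedule. Counted from the start of radiotherapy, the scheduled 6-month visit for HVLT-R, TMT and COWA is at about weeks 30 to 33, which is 2 to 5 weeks outside. The week-24 ANCOVA for these tests would then consist mainly of mistimed visits.

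The size depends on two assumptions that the SAP should settle: the origin of week 24, and whether six months means 24 or 26 weeks. Counted from the end of radiotherapy, there is no mismatch. No corrected power figure can be given, because the documents do not say how many of the 94 patients have a paper test in the window. This is a correction that should be made. It does not touch the primary endpoint.

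**What to change.** In SAP 9.2, state the origin of week 24 and map each instrument to an analysis visit:

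- BAC: week 24 ± 4 weeks from the start of radiotherapy.
- HVLT-R, TMT and COWA: the scheduled 6-month visit after radiotherapy, with its own ± 4 week window, stating how many weeks six months stands for.

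In SAP 9.4.2, report evaluable patients by instrument and arm, and say which instrument the 94 patients (52 and 42) and the 17.6 units refer to.

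The cost is SAP wording and a recount of data already collected. One small drawback remains: with a 6-week course, the BAC result (nominally week 24) and the paper-test result (week 30 or 32) refer to time points about 30 − 24 = 6 to 32 − 24 = 8 weeks apart, which the report should state.

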9.3 METHOD OF ANALYSIS

For the analysis of change in cognition between baseline and week 24, an analysis of covariance (ANCOVA) will be conducted to compare treatment groups within the treated patient cohort. The outcome of this model is change in cognitive function. Treatment group assignment will be included in the model as a predictor, and the baseline measure of cognitive function will be included as a covariate.

As noted earlier, a significant amount of the follow-up cognitive assessments may be missing due to health decline, disease progression, and death. Much of the missing data is due to a subject permanently dropping out of the longitudinal assessment. A linear random coefficient model stratified by drop-out pattern will assess whether cognitive changes over time are consistent across treatment groups and drop-out patterns. This pattern-mixture model accounts for within subject correlation of longitudinal assessments.

If assumption for conducting either the ANCOVA model or the pattern mixture model are not satisfied, alternative approaches to analyses may be conducted. Options include transformation of the outcome data, as well as use of nonparametric methods.

Given that numerous endpoints will be examined that relate to cognition, adjustments for multiple comparisons (e.g., false discovery rate methods or Bonferroni) may be considered.

